3.0 Introduction

The Adherence to biological medication in Rheumatoid Arthritis (RA), Psoriatic Arthritis (PsA), Ankylosing Spondylitis (AS), plaque psoriasis (PsO), Crohn's disease (CD) and ulcerative colitis (UC):

As there exist a lot of variations in the definitions and methodologies of measurement used to characterize adherence - compliance and persistence - first of all it is important to provide a definition for these terms. Compliance or more precisely medication compliance refers to the extent a patient is passively following the physician's orders as acting in accordance with the prescribed timing, frequency and dosage. It is typically measured as a percentage of total number of doses taken in relation to the time period of observation, during which medication compliance is measured ^{1,2}. In the literature an arbitrary cut-off value of 80% is used to distinguish between compliance and non-compliance although it is not clear what the clinically relevant cut-off point is. It is also understandable that the required drugs which are necessary to achieve an optimal treatment goal may be different for each patient and each drug. Therefore some patients may be well controlled with a standard dosage scheme while other patients may require a more frequent administration. Persistence or more precisely medication persistence is the duration of time from the beginning to the discontinuation of the prescribed therapy and is measured in units of time ^{1,2}. Adherence can be considered as an umbrella term for medication compliance and medication persistence as this term involves both perceptions of taking a medication, namely regularity and consistency ^{1,2}. Poor or non-adherence to a drug is a very important aspect in contributing to inadequate response to or failure of treatment and worsening of the disease. In consequence of an insufficient adherence clinical outcomes will deteriorate and may prompt a physician to further diagnostic procedures and eventually to an unnecessary change in medication³. Clearly this may lead to a longer patient recovery period and increased healthcare costs. This raises the question: how can we improve adherence in those patients who are afflicted with chronic inflammatory diseases like RA, AS, PsA, PsO, CD or UC? The answer is not easy because adherence is a complex phenomenon and it can both be difficult to identify factors associated with nonadherence and applying help in an effective manner. In clinical studies about tight control such factors can be easier identified and patients can therefore be more intensively motivated to be

compliant and continue their treatment (persistence). Although on the contrary in routine clinical practice such a tight control is hardly possible, medical aid for the optimization of treatment adherence should as far as possible be tailored to individual's primary reasons and concerns (e.g. worries of potential adverse events of biological treatment) for not taking a drug. In this context, patients' attitudes to treatment play an important role for adherence – mainly due to the fact that attitudes are varying.

4.0 Rationale

The aim of this non-interventional post-marketing observational study (PMOS) is to assess RA, PsA, AS, PsO, CD and UC patients' adherence attitudes (beliefs), currently being managed in a specialist rheumatology, dermatology or gastroenterology practice or respective hospital department, to maintenance therapy with a scheduled Adalimumab monotherapy or a combination therapy with methotrexate and to investigate whether there are correlations between such beliefs and adherence to maintenance treatment. For the assessment of RA, PsA, AS, PsO, CD or UC patients attitudes/beliefs to their scheduled maintenance treatment and medicine in general we are going to use the Beliefs about Medicines Questionnaire (BMQ)⁴ at the beginning of this study. In order to identify RA, PsA, AS, PsO, CD or UC patients at risk for non-adherence in due time in the course of this study the Morisky Medication Adherence Scale (MMAS)⁵ shall be used. In this context it is also of interest to evaluate patients' treatment satisfaction during Adalimumab monotherapy or combination therapy with methotrexate for which reason the Treatment Satisfaction Questionaire for Medication (TSQM)^{6,7} is used. As part of clinical practice the laboratory parameters ESR and/or CRP will be measured as an indication for disease activity. Furthermore the degree of disease activity has certainly a significant impact of treatment adherence for which reason the Rheumatoid Arthritis Disease Acitivity Index (RADAI) for RA and if reasonable for PsA patients, the Bath Ankylosing Activity Index (BASDAI) for AS patients, the Psoriasis Area and Severity Index (PASI)^{10,11} for plaque psoriasis, Harvey-Bradshaw Index (HBI)¹² for CD patients and the Partial Mavo score (PMS)¹³ for UC patients shall be used.

P13-562 Protocol

Remark: A patient support program is not offered or scheduled by the sponsor. As this is a noninterventional study all decisions are up to a participating physician. A physician may offer a patient support program to a patient anyhow. As this might affect study results a respective question is incorporated in the eCRF.

Adalimumab \cap

The fully human (100% human peptide sequences) recombinant monoclonal IgG1 antibody adalimumab has been approved in combination with methotrexate for the treatment of moderate to severe, active rheumatoid arthritis in adult patients when the response to disease-modifying anti-rheumatic drugs including methotrexate has been inadequate and for the treatment of severe active and progressive rheumatoid arthritis in adults not previously treated with methotrexate⁸. In case of incompatibility against methotrexate or continuing treatment with methotrexate is considered as not appropriate, adalimumab can also be administered as a monotherapy. Adalimumab in combination with methotrexate is also indicated for the treatment of active polyarticular juvenile idiopathic arthritis, in children and adolescents aged 13 to 17 years who have had an inadequate response to one or more disease-modifying anti-rheumatic drugs (DMARDs). Adalimumab can be given as monotherapy in case of intolerance to methotrexate or when continued treatment with methotrexate is inappropriate. Adalimumab is also indicated for the treatment of adults with severe active ankylosing spondylitis who have had an inadequate response to conventional therapy and for the treatment of active and progressive psoriatic arthritis in adults when the response to previous disease-modifying anti-rheumatic drug therapy has been inadequate. Moreover, adaliumumab is indicated for the treatment of moderate to severe chronic plaque psoriasis in adult patients who failed to respond to or who have a contraindication to, or are intolerant to other systemic therapy including cyclosporine, methotrexate or PUVA⁸.

In gastroenterology, adalimumab is indicated for treatment of moderately to severely active Crohn's disease, in adult patients who have not responded despite a full and adequate course of therapy with a corticosteroid and/or an immunosuppressant; or who are intolerant to or have

Confidential Information No use or disclosure outside AbbVie is permitted without prior written authorization from AbbVie

P13-562 Protocol

medical contraindications for such therapies, as well as for treatment of moderately to severely active ulcerative colitis in adult patients who have had an inadequate response to conventional therapy including corticosteroids and 6- mercaptopurine (6-MP) or azathioprine (AZA), or who are intolerant to or have medical contraindications for such therapies⁸.

The recommended dose for adults in patients with rheumatoid arthritis is 40 mg Adalimumab administered every two weeks as single dose via subcutaneous injection. Methotrexate should be continued during treatment with adalimumab. The recommended dose of Adalimumab for patients with ankylosing spondylitis and for patients with psoriatic arthritis is 40 mg adalimumab administered every other week as a single dose via subcutaneous injection.

The recommended dose of Adalimumab for adult patients with plaque psoriasis is an initial dose of 80 mg administered subcutaneously, followed by 40 mg subcutaneously given every other week starting one week after the initial dose.

For adult patients with moderately to severely active Crohn's disease an induction dose regimen is 80 mg at Week 0 followed by 40 mg at Week 2. In case there is a need for a more rapid response to therapy, the regimen 160 mg at Week 0, 80 mg at Week 2, can be used. After induction treatment, the recommended dose is 40 mg every other week via subcutaneous injection. Some patients who experience decrease in their response may benefit from an increase in dosing frequency to 40 mg Adalimumab every week. The recommended Adalimumab induction dose regimen for adult patients with moderate to severe ulcerative colitis is 160 mg at Week 0 and 80 mg at Week 2. After induction treatment, the recommended dose is 40 mg every other week via subcutaneous injection. Some patients who experience decrease in their response may benefit from an increase in dosing frequency to 40 mg Adalimumab every week⁸. Indistinguishable in structure and function from naturally occurring human immunoglobulin G1 (IgG1) Adalimumab has been estimated to have a terminal half-life of 10-14 days ⁹. Because of the linear pharmacokinetic of Adalimumab it allows to be self-administered by either a pre-filled syringe or an autoinjection pen.

5.0 Study Objectives

5.1 Main objectives

The main purpose of this study is to assess patients' adherence attitudes (beliefs) to the maintenance therapy with a scheduled Adalimumab monotherapy or a combination therapy with methotrexate and to investigate whether there are correlations between such beliefs and adherence to maintenance treatment. In order to measure such beliefs the following questionnaire is used:

 Changes in the Beliefs about Medicines Questionnaire (BMQ) at 12 months compared to baseline. In addition, the correlations between beliefs and adherence to treatment will be done at baseline and at 12 months

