5.2 Secondary objectives

- Changes in the Morisky Medication Adherence Scale (MMAS) at 12 months compared to month 3,
- Changes of the Treatment Satisfaction Questionaire for Medication (TSQM) over time,
- Changes in Rheumatoid Arthritis Disease Activity Index (RADAI) in patients with RA and if reasonable in patients with PsA,
- Changes in Bath Ankylosing Spondylitis Disease Activity Index (BASDAI) in patients with AS,
- Changes in Psoriasis Area and Severity Index (PASI) in patients with plaque psoriasis,
- Changes in Harvey-Bradshaw Index (HBI) for patients with CD,
- Changes in Partial Mayo Score (**PMS**) for patients with UC,
- Changes of the C-reactive protein (CRP) over time
- Changes of the Erythrocyte sedimentation rate (ESR) over time

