6.5.2.2 Follow-up visits

The total treatment period is max. 12 months for each patient.

Approximately 4 follow-up visits are expected over the 12 months period. These visits should occur at an interval of 3 months - "V2", "V3", "V4", "V5".

The visit schedule is to be decided by the investigator according to the routine clinical practice. Intercurrent visits will be documented using the CRF module with the next following visit

number, Visits V2,V3,V4,V5.

Follow up visits shall comprise the following:

V2: ESR,CRP, MMAS, TSQM, RADAI, BASDAI, PASI, HBI, PMS concomitant treatment, Adalimumab-application

- V3: ESR,CRP, MMAS, TSQM, RADAI, BASDAI, PASI, HBI, PMS concomitant treatment, Adalimumab application
- V4: ESR,CRP, MMAS, TSQM, RADAI, BASDAI, PASI, HBI, PMS concomitant treatment, Adalimumab application
- **V5:** ESR,CRP, BMQ, MMAS, TSQM, RADAI, BASDAI, PASI, HBI, PMS concomitant treatment, Adalimumab-application, final statement

Evaluation of the tolerability of the Adalimumab treatment

Any serious adverse events (**SAEs**) of the Adalimumab regimen will be collected throughout this study and 70-days following the last dose of Adalimumab.

Evaluation of the durability of the Adalimumab treatment

Any changes to RA, PsA, AS, PsO, CD or UC treatment and the type of change (dose modification or discontinuation) will be recorded in the data report form, whether the modifications relate to the use of Adalimumab or to the use of concomitant RA, PsA, AS, PsO, CD or UC treatments. If Adalimumab is temporarily interrupted or permanently discontinued before the end of the planned observational period of 12 months, the reason for interruption/discontinuation and the details on the subsequent RA, PsA, AS, PsO, CD or UC treatment, if applicable, will be recorded.

The next routine follow-up visit will be the post interruption/discontinuation visit (see 6.5.1.3).

6.5.2.3 Follow-up visit after temporary interruption or early permanent discontinuation of the Adalimumab treatment (Post interruption / discontinuation visit)

Follow-up visits after temporary interruption or early permanent discontinuation shall comprise the following:

ESR,CRP, Beliefs about Medicines Questionnaire (BMQ), Morisky Medication Adherence Scale (MMAS), Treatment Satisfaction Questionnaire for Medication (TSQM), concomitant treatment, Adalimumab application, final statement.

Evaluation of the tolerability since the interruption/discontinuation of the Adalimumab treatment

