11.0 Data Analysis Plans

11.1 End points

11.1.1 **Primary end point**

Patients' adherence attitudes (beliefs) to maintenance therapy with a scheduled Adalimumab monotherapy or a combination therapy with methotrexate will be assessed at baseline (visit 1 =screening) and at the end of the study at visit 5. Furthermore it shall be investigated whether there are correlations between such beliefs and adherence to maintenance treatment.

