11.1.2. Secondary end points

As secondary endpoints the following parameters will be evaluated: changes in the Morisky Medication Adherence Scale (**MMAS**) at visit 2, 3, 4 and 5, changes in the Treatment Satisfaction Questionnaire for Medication (**TSQM**) at visit 2, 3, 4 and 5, changes at the laboratory parameters such as C-reactive protein (**CRP**) and Erythrocyte sedimentation rate (**ESR**).

Changes in the Rheumatoid Arthritis Disease Activity Index (**RADAI**), Bath Ankylosing Activity Index (**BASDAI**), Psoriasis Area and Severity Index (PASI), Harvey-Bradshaw Index (HBI) and the Partial Mayo score (PMS) at visit 2, 3, 4 and 5. The quality of the analyses will depend on the fact that laboratory measurements are not stringent in the context of a non-interventional observational study. Tolerability and safety will be assessed by collection and classification of serious adverse events. Serious adverse reactions observed on treatment with Adalimumab will be described. The duration on treatment with Adalimumab until development

of a serious adverse reaction leading to Adalimumab discontinuation or until escape from treatment will be measured.

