11.2.2 Reason for switch to HUMIRA[®]

Never achieved satisfactory response:	У	n
Achieved satisfactory response initially, but lost it over time:	у 🗌	n
Discontinued treatment due to intolerance/side effect(s) :	у 🗆	n

Others

HUMIRA (Adalimum: For each vi	ab)
ESR (mm / 1 hr) (Erythrocyte Sedimentation Rate)	CRP (mg/l) (C-Reactive Protein)

Confidential Information No use or disclosure outside AbbVie is permitted without prior written authorization from AbbVie

P13-562 Protocol

Adalimumab

For Visit 1, Visit 5, and as appropriate for Early Termination 10-item Beliefs about Medicines Questionnaire (BMQ)

We would like to ask you about your personal views about your medicine and medicine in general. Please circle how you feel about each of the statements. There is no right or wrong answer, we are interested in your personal views.

Score:1-5 1. My health, at present, depends on my medicines **Confidential Information** No use or disclosure outside AbbVie is permitted without prior written authorization from Version: 6.5; 27 Oct 2016 Page 79 of 110

a. Strongly disagree b. disagree c. uncertain d. agree e. strongly agree

- My life would be impossible without my medicines
 a. Strongly disagree b. disagree c. uncertain d. agree e. strongly agree
- Without my medicines I would become very sick
 a. Strongly disagree b. disagree c. uncertain d. agree e. strongly agree
- 4. My health in the future will depend on my medicines
 a. Strongly disagree b. disagree c. uncertain d. agree e. strongly agree
- My medicines protect me from becoming worse
 a. Strongly disagree b. disagree c. uncertain d. agree e. strongly agree
- Having to take medicines worries me
 a. Strongly disagree b. disagree c. uncertain d. agree e. strongly agree
- 7. I sometimes worry about the long term effects of my medicines
 a. Strongly disagree b. disagree c. uncertain d. agree e. strongly agree
- My medicines are a mystery to me
 a. Strongly disagree b. disagree c. uncertain d. agree e. strongly agree
- 9. My medicines disrupt my life
 a. Strongly disagree b. disagree c. uncertain d. agree e. strongly agree
- I sometimes worry about becoming too dependent on my medicines
 a. Strongly disagree b. disagree c. uncertain d. agree e. strongly agree

Total 10-item BMQ Specific Score:

Adalimumab For Visit 2, Visit 3, Visit 4, Visit 5, and as appropriate for Early Termination Morisky Medication Adherence Scale (MMAS)

Patient self-reported Medication-taking-Scale: Scoring: high-low;

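### The main belief-adherence correlation is planned at baseline, where no MMAS is taken, and no stated analysis relates Visit 1 beliefs to the adherence that follows

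*Combined protocol and SAP*

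**What the plan says.** Section 5.1 names two time points for the association: "In addition, the correlations between beliefs and adherence to treatment will be done at baseline and at 12 months". The primary endpoint in 11.1.1 repeats the aim without a measure, visit or method: "Furthermore it shall be investigated whether there are correlations between such beliefs and adherence to maintenance treatment".

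The form headings in Appendix D fix when each scale is completed. The BMQ form is marked "For Visit 1, Visit 5, and as appropriate for Early Termination" and the MMAS form "For Visit 2, Visit 3, Visit 4, Visit 5, and as appropriate for Early Termination". The Schedule of Activities in 6.5 agrees. Section 6.5.2.2 lists both scales among the Visit 5 items: "ESR,CRP, BMQ, MMAS, TSQM, RADAI, BASDAI, PASI, HBI, PMS concomitant treatment, Adalimumab-application, final statement".

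The MMAS scores from Visits 2 to 4 have a stated use only as secondary change endpoints. Section 5.2 takes the change "at 12 months compared to month 3", and 11.1.2 lists MMAS changes at Visits 2 to 5.

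Section 4.0 places the BMQ at the start of the study and brings in the MMAS with this purpose: "In order to identify RA, PsA, AS, PsO, CD or UC patients at risk for non-adherence in due time in the course of this study".

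**The concern.** The belief-adherence association is the second half of the main objective, yet one of its two planned time points has no MMAS. Whoever runs the analysis must drop the baseline correlation, substitute another adherence record, or choose a later MMAS after seeing the data. The only ordinary visit with both scales is Visit 5. A correlation there mixes two explanations: beliefs may have shaped adherence, or a year of treatment experience may have shaped beliefs.

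A prospective question can be answered from data the study already collects, namely whether beliefs at the start go with later adherence. Nothing in the text commits the study to answering it.

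**Working it through.** **1. Which scale is available when** (6.5 Schedule of Activities, 6.5.2, Appendix D)

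| Scale | V1 | V2 | V3 | V4 | V5 | Early termination |
|---|---|---|---|---|---|---|
| BMQ | yes | no | no | no | yes | yes |
| MMAS | no | yes | yes | yes | yes | yes |

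The same-visit pairs are therefore Visit 5 and, for those who leave, early termination. Visit 1 has none.

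**2. Whether another adherence record fills the Visit 1 gap.** Appendix D also records injection dates at each visit and a physician's adherent/non-adherent statement. The statement belongs to the final visit. Section 6.1.1 admits patients prescribed adalimumab up to 30 days before screening, and 6.1.2 excludes earlier adalimumab treatment. At Visit 1 there is thus at most about 30 days of adalimumab history from which adherence could be judged. A baseline correlation in the strict sense has little to work with on any of these measures.

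**3. Planned size.** Section 6.2 gives 80 + 30 + 30 = 140, and 28 sites × 5 = 140. The two agree. The documents give no alpha, power, target correlation or dropout rate. For scale, take an assumed observed correlation r = 0.20 and the Fisher interval tanh(atanh r ± 1.96/√(n − 3)):
- n = 140: 0.035 to 0.354
- n = 98 (assumed 30% loss): 0.002 to 0.383

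At this size the interval is wide, so extra precision from existing data is worth having.

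**4. What several later MMAS scores add to one.** The assumptions are that adherence is a stable trait measured with error, that Visit 1 BMQ relates equally to each later MMAS, and that the between-visit ICC is 0.4 to 0.9. None of these is in the documents. The reliability of a mean of k scores is k·ICC/(1 + (k − 1)·ICC). The observed correlation rises by √(reliability/ICC), which for k = 4 is √(4/(1 + 3·ICC)).

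| ICC | Reliability, k = 4 | Factor | r = 0.20 becomes |
|---|---|---|---|
| 0.4 | 0.727 | 1.35 | 0.270 |
| 0.6 | 0.857 | 1.20 | 0.239 |
| 0.8 | 0.941 | 1.09 | 0.217 |
| 0.9 | 0.973 | 1.04 | 0.208 |

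**5. Whether this means the Visit 5 pair is weakened.** Suppose instead that MMAS follows a first-order autoregressive pattern with correlation ρ between successive visits, and that Visit 5 beliefs track only current adherence. The correlation of Visit 5 BMQ with the mean of Visits 2-5, divided by that with the Visit 5 MMAS alone, is [(ρ³ + ρ² + ρ + 1)/4] / √[(4 + 6ρ + 4ρ² + 2ρ³)/16].
- ρ = 0.5: 0.469/√0.516 = 0.65
- ρ = 0.9: 0.860/√0.881 = 0.92

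Here the single same-visit pair gives the larger correlation. This case concerns Visit 5 BMQ, not the Visit 1 BMQ used in the fix, but it shows that attenuation of the planned pair does not follow from the design.

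**The case against.** The strongest reply is that the text is silent rather than wrong. Neither 5.1 nor 11.1.1 names the MMAS as the correlation variable, no sentence excludes Visits 2-4, and 11.2 leaves detail to a later data analysis plan. The word baseline might mean Visit 1 beliefs against later adherence, which would have time order. This stands as a limit: the pairing is inferred from the schedule, and it cannot be said that the plan as a whole lacks time order. It does not remove the gap. The protocol still does not say which adherence variable, from which visit, enters a main-objective analysis.

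A second reply is that 4.0 attaches timely identification of at-risk patients to the MMAS, not to the belief correlation, so that sentence does not require a lagged analysis. That is fair. The case rests on the schedule and on 5.1.

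A third is that 11.2 rules out a working hypothesis, so power is a poor yardstick. That is accepted, and no power figure is used here. Estimates with confidence intervals still need a defined variable and visit.

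A reader might go further and infer that the month-12 correlation is pulled towards zero by noise in one MMAS score and loses everyone who leaves before Visit 5. The documents support neither inference. A same-visit pair can be stronger than a correlation with averaged scores (step 5 of the working), and shared self-report at one visit may inflate it. BMQ and MMAS are both scheduled at early termination, so patients who leave and attend that visit can supply a pair; only those lost without it cannot.

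**Conclusion.** The point holds as a gap in definition and timing. Taking the MMAS as the adherence measure, the planned baseline correlation has no same-visit partner, the 12-month correlation is cross-sectional, and no stated analysis links Visit 1 BMQ to the MMAS scores that follow. This conclusion needs no assumption about noise or effect size.

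The statistical gain from using all later scores rather than one is conditional: a factor of about 1.04 to 1.35 under the assumed ICCs and a stable trait. It is not an estimate of bias in the month-12 correlation and should not be reported as one. The main benefits are time order, a pre-specified variable, and use of partial follow-up from patients with some MMAS but no Visit 5. The change is a cheap and worthwhile improvement to half of the main objective.

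**What to change.** In 5.1, 11.1.1 and the data analysis plan:

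- Name the MMAS as the adherence variable for the correlation, or name whichever other record is intended.
- Replace the baseline correlation with the association of Visit 1 BMQ with all available later MMAS scores (Visits 2-5 and early termination). Use either a Spearman correlation with each patient's mean MMAS and a 95% confidence interval, or a proportional-odds model with a patient random effect and visit as a factor. Choose one before analysis, and state how early-termination scores are placed in time.
- Keep the same-visit month-12 correlation as a separate result, labelled cross-sectional.

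The cost is a few lines of text and no new data collection. The downside is a change in what is described: the new result concerns average adherence over months 3 to 12, not the state at month 12, which is why the month-12 correlation should stay alongside it.
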